3.5.3. STUDY SAFETY

All adverse events will be recorded, described, and compared for Cementless vs. Control groups. Comparisons will use standard statistical tests (chi-square, Fisher's exact). Adverse events resulting in device removal and/or revision and those not requiring device removal and/or revision will be summarized. Device related serious adverse events will be collected and evaluated for differences across the control and experimental population.

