2.11 PRIMARY AND SECONDARY STUDY ENDPOINTS

The study's primary safety and efficacy endpoints for the Oxford® Cementless Partial Knee System will include:

• Radiographic Success at 22+ months Study ID: ORTHO.CR.US30

- Absence of Revision/Removal/UADE at any time point
- The Knee Society Assessment Score at 22+ months
- The Knee Society Function Score at 22+ months

The study's secondary endpoints include:

- The Knee Society Assessment Score at all time points other than 22+ months
- The Knee Society Assessment Score for bilateral subjects at all time points
- The Knee Society Function Score at all time points other than 22+ months
- The Knee Society Function Score for bilateral subjects at all time points
- The Oxford Knee Score at all time points
- Radiographic Success at all other time points
- Single question assessment of patient satisfaction at all time points^a

The safety of the system will further be monitored by recording and reporting adverse events [including serious adverse events not considered UADEs throughout the follow-up period].

Safety data will be summarized as follows:

- Device removals or revisions
- Unanticipated adverse device events
- Systemic adverse events
- Local adverse events
- Reoperations and Other Interventions

Any patient who fails to return for multiple, consecutive, scheduled follow-up visits for any reason other than the criteria listed above will be identified as Missing Data.

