3.1.1. RADIOGRAPHIC SUCCESS

The proportion of radiographically successful knees in the Cementless group is non-inferior to the proportion of radiographically successful knees in the Control group using an 8% margin of non-inferiority. The test is based on the upper bound of a one-sided 95% confidence interval for the difference, Control minus Cementless, of proportions of success at 22+ months. A conclusion of non-inferiority is supported if the upper bound of the confidence interval is 0.08 or less. In addition, a Fisher's Exact p-value will also be computed to test this hypothesis.

In this analysis, each knee will be considered as a separate case, and unilateral and bilateral subjects will be analyzed together, providing the unilateral and bilateral groups are poolable per sensitivity analyses given in Section 3.1.5°.

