3.1.2. ABSENCE OF REVSION/REMOVAL/UADE

Using a 10% margin of non-inferiority, the proportion of knees who are free of Revision/Removal/UADE during the course of the study in the Cementless group is non-inferior to the proportion of such knees in the Control group. The test is based on the upper bound of a one-sided 95% confidence interval for the difference, Control minus Cementless, of success proportions. A conclusion of non-inferiority is supported if the upper bound of the confidence interval is 0.10 or less. In addition, a Fisher's Exact p-value will also be computed to test this hypothesis.

^b Dmitrienko, Alex, et al. *Analysis of Clinical Trials Using SAS*. SAS Publishing, 2005, pp 75-76.

^c As agreed at FDA pre-submission meeting Q160425 April 13, 2016.

In this analysis, each knee will be considered as a separate case, and unilateral and bilateral subjects will be analyzed together, providing the unilateral and bilateral groups are poolable per sensitivity analyses given in Section 3.1.5^d.

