3.5.4. Analyses of Secondary Outcomes

These outcomes include the primary study endpoints at times other than two years. In addition, a composite success/failure endpoint consisting of the four primary outcomes will be tested for non-inferiority, Cementless vs. Control, using a non-inferiority margin of 10%. In this composite, the threshold for success for the Knee Society Assessment and Function scores will be 80 points. A composite success outcome requires a successful outcome for all four components.

In addition, at all-time points, implant revisions or removals will be described by Kaplan-Meier time-to-failure curves and compared using log-rank tests. Mean Knee Society Assessment Score, Knee Society Function Score, and Oxford Knee scores will be displayed by time point and compared between treatment groups. Analyses will be performed using standard statistical tests and will be chosen as appropriate for the scale and distribution of

the measures being analyzed (chi-square, Cochran-Mantel-Haenszel chi-square, Student's t).

Bilateral patients will be analyzed as a separate group for purposes of secondary analyses of Knee scores at each time point as well in the secondary analysis of composite success rates. For other analyses, including radiographic and safety outcomes, bilateral and unilateral patients will be analyzed together.

Secondary outcomes will be analyzed using all patients with available data for the endpoint being analyzed. As with the primary analysis, the secondary analyses will use the device that was actually implanted if it was a study device; if a study device is not received, the patient will not be included in the secondary analyses.

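### Section 3.5.3 compares adverse events only by tests of equality, with no estimate of the excess or interval, so for uncommon events a non-significant result cannot show comparable safety.

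*Combined protocol and SAP*

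**What the plan says.** Section 3.5.3 (Study Safety) sets the scope: "All adverse events will be recorded, described, and compared for Cementless vs. Control groups". It then names the method: "Comparisons will use standard statistical tests (chi-square, Fisher's exact"). For the serious device-related events it says: "Device related serious adverse events will be collected and evaluated for differences across the control and experimental population". It gives no effect measure, confidence interval, significance level, sidedness, expected rate or power for any of these.

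Section 3.5.4 adds that "implant revisions or removals will be described by Kaplan-Meier time-to-failure curves and compared using log-rank tests", again without an effect estimate or interval.

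Elsewhere the plan does bound how much worse the new device may be. Section 3.1.2 (revision, removal or UADE) ends: "A conclusion of non-inferiority is supported if the upper bound of the confidence interval is 0.10 or less". Section 3.1.1 (radiographic success) uses the "upper bound of a one-sided 95% confidence interval for the difference, Control minus Cementless, of proportions of success at 22+ months" with a margin of 8 points. Section 2.11 places the remaining adverse events outside those endpoints: "The safety of the system will further be monitored by recording and reporting adverse events". Appendix B (Follow Up) claims that the follow-up period is long enough to give accurate rates of known or suspected adverse events.

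**The concern.** The safety question for a modified device against an approved one is how large an excess of harm the data still allow. Sections 3.1.1 to 3.1.4 ask that question and answer it with a one-sided bound. Section 3.5.3 asks only whether a difference can be detected. When events are few, failing to detect one is the likely result whether or not there is an excess.

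The gap covers real events. A UADE must be unanticipated in nature, severity or degree of incidence (section 2.5), so the risks already listed in sections 4.1 to 4.3, such as infection or venous thrombosis, will generally not be UADEs. A reoperation is defined in section 2.5 so as to exclude revision and removal. For anticipated device-related SAEs treated without revision or removal, and for reoperations, there is generally no co-primary bound to fall back on. A real excess in them could be tabulated with a non-significant p-value and no statement of the excess that remains compatible with the data. The accuracy that Appendix B claims for adverse event rates would also have no measure attached to it.

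**Working it through.** **1. The plan's own sample size.** Section 3.3 assumes 95% success in both arms, a margin of 0.08, alpha 0.05, 90% power and 2:1 allocation. With unpooled variances,

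n(Control) = (1.645 + 1.282)² × 0.95 × 0.05 × (1 + 1/2) / 0.08² = 8.57 × 0.07125 / 0.0064 ≈ 95.4, so 96, with 192 Cementless.

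The Farrington-Manning form gives 94 and 188. The plan states 96 and 191, so its figure reproduces to within 3%, at one-sided 0.05. Inflation by 10% plus 15% gives 191/0.75 = 254.7 and 96/0.75 = 128, which is the stated 255 vs 128. This calculation concerns radiographic success. No corresponding calculation exists for adverse events.

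**2. Inputs for the safety tests.** Group sizes are 255 vs 128 from section 3.3, or 217 vs 109 after 15% attrition (255 × 0.85 = 216.75; 128 × 0.85 = 108.8). A two-sided 0.05 level is an assumption, because section 3.5.3 gives none. Event rates are assumptions, because the documents give no AE, SAE or revision rate. Knees are treated as independent.

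**3. Chance of finding Cementless significantly worse.** With X ~ Bin(255, p_I) and Y ~ Bin(128, p_C),

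power = sum over all (x, y) of P(X = x) P(Y = y), counted where x/255 > y/128 and the test gives p ≤ 0.05.

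| Control to Cementless | 255 vs 128: Fisher / chi-square | 217 vs 109: Fisher / chi-square |
|---|---|---|
| 1% to 2% | 2% / 4% | 1% / 2% |
| 2% to 4% | 11% / 14% | 8% / 12% |
| 3% to 6% | 19% / 21% | 16% / 18% |
| 5% to 10% | 35% / 38% | 29% / 32% |
| 10% to 20% | 70% / 73% | 62% / 65% |
| 20% to 40% | 98% / 98% | 96% / 96% |
| 5% to 15% (tripling) | 85% / 88% | 78% / 81% |

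Power for a doubling passes 50% at a Control rate of about 6.7% (7.7% after attrition) and 80% at about 11.7% (13.3%).

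**4. What an interval would add.** Take 13/255 vs 2/128 events, that is 5.1% vs 1.6%, a difference of 3.54 points. Fisher gives p = 0.16 and chi-square p = 0.092. The standard error is √(0.051 × 0.949/255 + 0.0156 × 0.9844/128) = 0.0176, so the one-sided 95% Wald upper bound is 0.0354 + 1.645 × 0.0176 = 0.064. Neither p-value tells the reader that an excess of 6.4 points is still compatible with the data.

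**5. Precision that can be expected at 255 vs 128 (Wald, two-sided 95%).** Equal 2% rates give ±3.0 points and equal 5% rates ±4.6. An observed 2% vs 4% gives +2.0 (−1.4 to +5.4). An observed 5% vs 10% gives +5.0 (−0.3 to +10.3).

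**6. Revision curves.** By Schoenfeld's approximation, z = √(events × 2/9) × ln(HR) − 1.96. With 2% Control revisions and a hazard ratio of 2, events = 128 × 0.02 + 255 × (1 − 0.98²) = 12.7, so z = 1.16 − 1.96 = −0.80 and power is 21%. At 5% Control revisions it is 45%. With a hazard ratio of 3, power is 58% and 92%. The approximation is rough with so few events.

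**The case against.** The strongest reply is that device safety is largely bounded already. Revisions and removals enter the section 3.1.2 co-primary and the section 3.5.4 composite, and a revision before two years also counts as a radiographic failure (section 3.5.5). Component fracture, migration over 3 mm and osteolysis are radiographic failures whether or not the implant is removed. Exchanging a bearing counts as a revision under section 2.5. A known event type with unexpected severity or incidence can qualify as a UADE. All of this stands, and it confines the gap mainly to anticipated device-related SAEs without revision or removal, other adverse events, and reoperations. The UADE route is a limited safeguard, because the documents supplied state no expected incidence to judge against.

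A reader might infer that every safety comparison outside section 3.1.2 misses a doubling or more of harm most of the time. The documents do not support that. The table shows good detection of a doubling of common events and of a tripling from 5%. Section 2.9.5 reports so many entries for normal early post-operative symptoms that some adverse event categories may well be common. A reader might also infer that the revision curves rest on the log-rank test alone. They do not, since section 3.1.2 bounds the same events.

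It is also fair to say that nothing in the plan states that a non-significant p-value will be taken as equal safety, and that arm-level counts would let a reader compute an interval. Both points limit the harm. They do not make the equality test the right summary.

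**Conclusion.** The point holds for uncommon events. Where the Control rate is about 5% or less, the section 3.5.3 tests detect a doubling less than half the time: 2% to 38% across Control rates of 1% to 5% at full enrolment, and lower after attrition. A non-significant result there cannot show comparable safety. The figures rest on assumed event rates, an assumed two-sided 0.05 level and independent knees. The recommendation does not depend on the rates, because an equality test reported without an interval never shows how much excess the data allow.

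The primary success decision is unaffected. This is a worthwhile, nearly free improvement to the safety reporting and not a flaw in the primary inference.

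**What to change.** In section 3.5.3, for any AE, any SAE, device-related SAEs and reoperations, report the risk difference (Cementless minus Control) with a two-sided 90% or 95% score interval beside any p-value. The upper limit of the 90% interval corresponds to the one-sided 95% bound used in section 3.1.2. A score interval is preferable to the Wald form when a group has only a few events. State that a non-significant p-value will not be read as evidence of equal safety. No new margin is needed.

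Optionally, in section 3.5.4, show the 24-month difference in Kaplan-Meier revision-free proportion with its interval beside the log-rank p-value. This is supplementary because section 3.1.2 already bounds revisions. It still adds information, because the 10-point margin would accept a rise in failures from 2% to 4% in 99.8% of trials and from 5% to 10% in 59%.

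The cost is SAP wording and a few table columns, with no new data and no change to sample size or the success rule. The downside is that wide intervals will be visible.

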3.5.4. Analyses of Secondary Outcomes

These outcomes include the primary study endpoints at times other than two years. In addition, a composite success/failure endpoint consisting of the four primary outcomes will be tested for non-inferiority, Cementless vs. Control, using a non-inferiority margin of 10%. In this composite, the threshold for success for the Knee Society Assessment and Function scores will be 80 points. A composite success outcome requires a successful outcome for all four components.

In addition, at all-time points, implant revisions or removals will be described by Kaplan-Meier time-to-failure curves and compared using log-rank tests. Mean Knee Society Assessment Score, Knee Society Function Score, and Oxford Knee scores will be displayed by time point and compared between treatment groups. Analyses will be performed using standard statistical tests and will be chosen as appropriate for the scale and distribution of

the measures being analyzed (chi-square, Cochran-Mantel-Haenszel chi-square, Student's t).

Bilateral patients will be analyzed as a separate group for purposes of secondary analyses of Knee scores at each time point as well in the secondary analysis of composite success rates. For other analyses, including radiographic and safety outcomes, bilateral and unilateral patients will be analyzed together.

Secondary outcomes will be analyzed using all patients with available data for the endpoint being analyzed. As with the primary analysis, the secondary analyses will use the device that was actually implanted if it was a study device; if a study device is not received, the patient will not be included in the secondary analyses.

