- 24. Patients who have received systemic steroids within the past 6 months or steroid injection into the affected knee within the previous 6 weeks prior to enrollment
- 25. Patients who are pregnant
- 26. Patients with severe valgus or varus knees (valgus or varus angulation of more than 20°) where collateral ligament, iliotibial band, or popliteal release is required
- 27. Patients who refuse to sign the IRB approved Informed Consent Form
- 28. Participation in an interventional clinical research study procedure, *other than a bilateral knee arthroplasty in this study*, within the past 12 months
- 29. Patients with a history of osteomyelitis or sepsis of the index knee
- 30. Patients who require patellar resurfacing
- 31. Patients who are not skeletally mature
- 32. Patients who have had a total hip replacement procedure <18 months prior to entering the study
- 33. Patients who have had a contralateral non-study knee replacement procedure <18 months prior to entering the study
- 34. Patients who are found intraoperatively to have inadequate bone stock or other conditions that contraindicate a partial knee replacement

NOTE: Patients implanted on the contralateral knee with the investigational or control device as part of their participation in the study are permitted to be enrolled in the study, but will receive a matching device to the original study knee and will not be randomized.

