3.0 STATISTICAL ANALYSIS PLAN

This is a two-group, multi-center, randomized clinical trial to compare Biomet's cemented Oxford® Partial Knee System to another active intervention, the Oxford® Cementless Partial Knee System (abbreviations: Control vs. Cementless). Imbalanced, blocked randomization (2:1, Cementless vs. Control) will be implemented.

Randomization will be per patient. In the event that an intraoperative screen failure occurs post-randomization, randomization will not be reassigned and this patient will not count toward the overall sample size. Randomization will continue with the next subject enrolled as previously described. The randomization plan will be produced using SAS v 9.2 for Windows. Randomization will be by center, and each site will receive separate randomization plans using a predetermined block size that will remain undisclosed to the sites. The randomization assignments will be in the form of envelopes to be opened intra-operatively after the first tibial cut and bone quality is assessed against the eligibility criteria.

The primary study endpoint will consist of four (4) individual co-primary endpoints, including both safety and efficacy measures. The following endpoints are included as individual parts of the primary endpoint:

- 1. Knee Society Assessment Score number of points received for the Knee Society Assessment Score at the 22+ month assessment
- 2. Knee Society Function Score number of points received for the Function Score at the 22+ month assessment.
- 3. Revisions or removals of any component of the device or an unanticipated, device-related adverse event (UADE) at any time point. This is a binary endpoint in which a knee is either a "success" or "failure". To obtain a successful result, a knee must reach the 22 + month upper window limit with the device intact and without a component revision/removal or a UADE.
- 4. Radiographic Assessments at the 22+ month assessment

This is a binary endpoint in which a knee is either a "success" or "failure". To obtain a successful radiographic endpoint, a knee must meet the following criteria at the 22+ month

- a. Absence of osteolysis
- b. No migration/subsidence of any femoral or tibial component
- c. Absence of fractured component

Conversely, a radiographic failure is defined as follows:

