3.1.5. SENSITIVITY ANALYSES - UNILATERAL AND BILATERAL KNEES

To address the impact of possible correlation occurring due to including two knees from the same patient, for the two endpoints that will incorporate bilateral knees (Radiographic Success and Absence of Revision/Removal/UADE), additional sensitivity analysis will be conducted in order to address any potential correlation occurring due to including two knees from the same patient. These are to include:

- a. An analysis that considers only unilateral subjects.
- b. A repeated measures model approach that can account for possible correlation within subjects.
- c. An analysis of data at the patient level, in which a patient is considered a "failure" if either knee fails.

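### If the secondary log-rank test on revision or removal is run per knee, nothing in Section 3.5.4 corrects for two same-device knees in one patient, so its standard error is slightly too small under positive correlation

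*Combined protocol and SAP*

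**What the plan says.** Under Section 3.5.4, "implant revisions or removals will be described by Kaplan-Meier time-to-failure curves and compared using log-rank tests". The same section sets the pooling rule: "For other analyses, including radiographic and safety outcomes, bilateral and unilateral patients will be analyzed together". It names no clustered variance and no patient-level rule, and does not say whether the unit is the knee or the patient.

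Three other places bear on the unit and the pairing:

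- Section 3.0: "Randomization will be per patient".
- The note closing Section 2.2: a patient whose second knee enters the study "will receive a matching device to the original study knee and will not be randomized".
- Section 3.1.2, on the binary primary endpoint that includes revision and removal: "In this analysis, each knee will be considered as a separate case, and unilateral and bilateral subjects will be analyzed together". That pooling is conditional on the unilateral and bilateral groups being poolable.

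Section 3.1.5 takes up within-patient correlation: "for the two endpoints that will incorporate bilateral knees (Radiographic Success and Absence of Revision/Removal/UADE), additional sensitivity analysis will be conducted". It lists a unilateral-only analysis, a patient-level analysis in which either knee's failure counts, and this: "A repeated measures model approach that can account for possible correlation within subjects".

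**The concern.** An ordinary log-rank test assumes independent units. Here the two knees of a bilateral patient are always in the same arm, so positive correlation between them adds to the variance of the arm comparison and does not cancel out of it. The sponsor recognises the issue in 3.1.5, yet the time-to-failure comparison, which also pools bilateral knees, is outside that section's scope and lacks the poolability condition set for the primary endpoint.

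At stake is the p-value of the plan's only time-to-event comparison of implant survival between the arms. If the correlation is ignored, chance differences in revision, in either direction, will be called significant somewhat more often than the nominal rate.

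**Working it through.** **The plan's own figures.** The documents give no event count, power or error rate for the log-rank test, so nothing specific to it can be reproduced. The sample size that supplies the knees does reproduce. With 95% success in both arms, margin 0.08, one-sided 5%, 90% power and 2:1 allocation, the normal approximation gives control n = (1.645 + 1.282)² × 0.0475 × 1.5 / 0.0064 = 95.3, that is 96, and cementless 2 × 95.3 = 190.7, that is 191. Allowing 10% plus 15%, (191 + 96) / 0.75 = 382.7, that is 383.

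**Inputs for the check.**

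- Bilateral share: 10%, from Sections 3.3 and 3.5.2. Neither says whether this is a share of knees or of patients, so both readings are used.
- Within-patient correlation of revision, ρ: not in the documents. Values from 0.2 to 0.8 are assumed, with 1.0 as the limit.
- Unit: the knee, inferred from Sections 3.0 and 3.1.2.
- Test: two-sided 5%. Section 3.5.4 states neither sidedness nor level, so this is also assumed.

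**Formula.** Let f be the share of knees that belong to bilateral patients. Among n knees in an arm, n(1 − f) are single with variance σ² each, and nf/2 pairs have variance 2σ²(1 + ρ) each. The total is nσ²(1 + fρ), so the design effect is DE = 1 + fρ. The true standard error is √DE times the ordinary one, and the actual level is 2[1 − Φ(1.96/√DE)].

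If 10% of knees are in pairs, f = 0.10. If 10% of patients are bilateral, f = 0.2/1.1 = 0.182.

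Example: f = 0.182 and ρ = 0.5 give DE = 1.091 and √DE = 1.044. Then 1.96/1.044 = 1.877, and the level is 6.1%.

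| ρ | DE, 10% of knees | SE ratio | Level | DE, 10% of patients | SE ratio | Level |
|---|---|---|---|---|---|---|
| 0.2 | 1.02 | 1.010 | 5.2% | 1.036 | 1.018 | 5.4% |
| 0.5 | 1.05 | 1.025 | 5.6% | 1.091 | 1.044 | 6.1% |
| 0.8 | 1.08 | 1.039 | 5.9% | 1.145 | 1.070 | 6.7% |
| 1.0 | 1.10 | 1.049 | 6.2% | 1.182 | 1.087 | 7.1% |

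**Simulation check.** The settings were 383 knees, 2:1 allocation, 10% of patients bilateral, 2 to 4 years of follow-up, an assumed 2-year revision risk of 5% or 10%, and 4,000 runs per setting. The ordinary log-rank test rejected in 4.7% of runs with no correlation, 5.2% to 6.0% at latent correlations of 0.3 to 0.6, and 7.1% at near-perfect correlation. The patient-clustered version stayed between 4.7% and 5.6%. Simulation error is about √(0.05 × 0.95/4000) = 0.3 percentage points. The latent correlation is not on the same scale as ρ, so only the range should be compared with the table.

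**The case against.** The strongest reply is that the plan never says this test is run per knee. The statement that each knee is a separate case belongs to the binary primary endpoint, while 3.5.4 speaks of patients. That stands as far as it goes: knee-level analysis is a strong inference, not a stated rule. But if the patient was meant, the section would still have to say so and define the failure time for someone with two knees.

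A second reply is that the comparison is secondary, has no margin, and tests for a difference, so a slightly liberal test flags a revision difference more readily and does not hide one. This also stands, and it limits the importance.

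A third is that the point is covered elsewhere. Section 3.1.5 gives essentially the same event three correlation-aware analyses as a binary endpoint, and Appendix B promises that assumptions will be checked and more suitable tests used if they fail. The first would help show whether clustering matters for revision. The second is generic and does not mention paired knees. Neither applies a correction to the log-rank test.

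Stronger readings that a reader might infer are not supported:

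- That Kaplan-Meier confidence intervals are too narrow: the plan specifies curves only and mentions no intervals or variance method for them.
- That this is the only analysis using the longer follow-up: Section 2.11 lists knee scores, radiographic success and satisfaction at other time points, with adverse events recorded throughout.

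**Conclusion.** The point holds as a minor gap. A knee-level log-rank test, pooled as 3.5.4 describes, ignores same-arm pairing, and the remedies in 3.1.5 do not reach it. With a 10% bilateral share and an assumed correlation of 0.2 to 0.8, the ordinary standard error should be about 1% to 4% larger if the 10% refers to knees, or 2% to 7% larger if it refers to patients. A nominal 5% test then runs at about 5.2% to 5.9%, or 5.4% to 6.7%.

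This rests on three assumptions: the knee is the unit, the correlation is positive, and the realised bilateral share is close to the planned one. With zero correlation there is no error. The documents do not support reading it as a threat to the primary conclusion: study success under Section 3.1 depends on the four co-primary endpoints, and this test is not among them. The Kaplan-Meier point estimates are not affected.

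**What to change.** Add to Section 3.5.4 that the unit for the time-to-failure analysis is the knee, and that the arms are compared by a log-rank or marginal Cox score test with variance clustered by patient. Any Kaplan-Meier intervals that are reported should use the same clustered variance.

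The alternative is time to first knee failure per patient, which matches item (c) of Section 3.1.5. That choice changes the quantity estimated, since a bilateral patient has two knees at risk, and it needs a stated time origin for staged procedures.

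The clustered option costs a sentence in the SAP and a standard software setting. It needs no new data and leaves the knee-level point estimates unchanged. The price is slightly larger standard errors.
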